7.7.6. Analyses of Other Endpoints

Endpoints listed in Section 7.3 for the RI period and the LTE will be descriptive in nature since there is no control arm. Summary statistics will be generated following the methodologies stated in Section 7.7. Analysis for efficacy endpoints measured at week 12 will be done using the run-in Week 12 analysis set.

Other analyses include anti-rilonacept antibodies and biomarker analyses. These analyses will be described in the SAP.

7.7.7. Pharmacokinetic Analyses

For all subjects, serum samples will be collected at time points shown in the Schedule of Activities in order to quantify concentrations of rilonacept. Descriptive statistics will be calculated for the serum concentrations of rilonacept by visit. Individual listings of serum concentrations will be provided.

Pharmacokinetic data may be used in a subsequent population PK evaluation that will be conducted outside of this study and described in a separate report.

7.7.8. Safety Analyses

Treatment-emergent AEs (TEAEs), defined as AEs that start or increase in severity after the first dose of study drug and before 6 weeks after the last dose of study drug, will be coded to system organ class and preferred term using the most recent version of MedDRA. TEAEs will be analyzed for all subjects combined and by treatment group in the RW period. Further analyses by severity and relationship to study drug as well as analyses of serious TEAEs will be presented.

Descriptive statistics will be used to summarize safety endpoints by visit for all subjects combined in the RI period and by treatment group in the RW period. Two-sided 95% CIs will be presented where meaningful. Data summaries will be displayed for clinical laboratory analyses (including safety laboratory measurements, ADAs, etc.), vital signs measurements, ECGs, and physical examination findings.

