2.2. Secondary Objective

The secondary objective of this study is to assess the safety of rilonacept treatment in subjects with recurrent pericarditis.

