3.1.3. Double-blind Placebo-controlled RW Period (pericarditis recurrence event-driven duration)

During the RW period, subjects who were able to stop background pericarditis medications and who achieve Clinical Response on rilonacept monotherapy at RI Week 12/RW baseline will be randomized 1:1 to double-blinded administration of study drug:

- Rilonacept 160 mg (or 2.2 mg/kg in pediatric subjects ≥ 12 and < 18 years old) SC injections once weekly OR
- Matching placebo SC injections once weekly

Pericarditis Recurrence in the RW Period: For the definition of pericarditis recurrence, refer to Section 6.2.3.

Upon pericarditis recurrence, subjects who report at least 1 day with pericarditis pain measurement ≥ 4 on the 11-point Numerical Rating Scale [NRS] and have 1 CRP value ≥ 1 mg/dL (either on the same day or separated by no more than 7 days) will receive **bailout rilonacept** (2 open-label injections of 160 mg rilonacept [or 4.4 mg/kg for pediatric subjects]) irrespective of randomized treatment assignment and as soon as at least 5 days have passed since the last study drug injection. The subjects transitioning to bailout rilonacept will remain blinded to their prior RW period treatment assignment. Sequential Oral Rescue Therapy (ORT), i.e., analgesics first, then NSAIDs, and then colchicine, can be added, if needed, at the discretion of the Investigator, as outlined in Section 5.6.3 and detailed in the Pharmacy Manual.

Subjects with pericarditis recurrence who do not meet the protocol criteria for bailout rilonacept will continue blinded study drug until they meet the protocol criteria for bailout rilonacept or through the end of the RW period. For those subjects, sequential ORT can be added to blinded study drug at the discretion of the Investigator, as outlined in Section 5.6.3 and detailed in the Pharmacy Manual.

All suspected pericarditis recurrence events in the RW period will be formally adjudicated by the Clinical Endpoint Committee (CEC), and only events that are confirmed by the CEC as pericarditis recurrences will be used in the Primary Endpoint analysis.

The RW period will continue until the prespecified number of primary efficacy endpoint (CEC-confirmed pericarditis recurrence) events has occurred. Based on projected event accrual and subject randomization, Kiniksa Pharmaceutical will determine the end of the RW period and announce to sites so that subject End of Randomized Withdrawal (EORW) visits

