4.2. Exclusion Criteria

Subjects meeting any of the following criteria will be excluded from the study:

1. Has a diagnosis of pericarditis that is secondary to specific prohibited etiologies, including tuberculosis (TB); neoplastic, purulent, or radiation etiologies; post-thoracic blunt trauma (e.g., motor vehicle accident); myocarditis; or systemic autoimmune diseases with exception of Still's disease.
2. Is pregnant, breastfeeding, or planning a pregnancy or fathering a child during the study or within 3 months after the last study drug administration.
3. Has a history of immunosuppression, including positive human immunodeficiency virus (HIV) test results.
4. Is currently receiving CS at a dose of >60 mg/day prednisone (or equivalent) for adult subjects, or >0.5 mg/kg/day (or >60 mg/day, whichever is lower) prednisone (or equivalent) in pediatric subjects (≥ 12 and <18 years old).
5. Has ever received cytotoxic drugs, including cyclophosphamide, chlorambucil, nitrogen mustard, or other alkylating agents.
6. Has ever received agents that deplete B or T cells (e.g., rituximab, alemtuzumab).
7. Has received systemic immunomodulatory agents (with exception of CS) within the following time frames prior to RI baseline (first administration of study drug):
 - a. Azathioprine, mycophenolate mofetil, cyclosporine, tacrolimus, sirolimus, or mercaptopurine within 24 weeks.
 - b. TNF inhibitors, IL-6 inhibitors, or janus-activating kinase inhibitors within 12 weeks.
 - c. Canakinumab within 12 weeks. Canakinumab could not have been discontinued due to safety unless it was discontinued due to local injection site reactions.
 - d. Rilonacept within 6 weeks. Rilonacept could not have been discontinued due to lack of efficacy or due to safety.
 - e. Methotrexate within 2 weeks.
 - f. Anakinra within 5 days. Anakinra could not have been discontinued due to lack of efficacy or due to safety unless it was discontinued due to local injection site reactions.
8. Has a history of myeloproliferative disorder.
9. Has a history of demyelinating disease or symptoms suggestive of multiple sclerosis.
10. Meets the following TB criteria:
 - a. History of active TB prior to screening OR
 - b. History of latent TB that was not adequately treated prior to screening OR

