6.2.3. Management of Suspected Pericarditis Recurrence in the RW Period

Pericarditis Recurrence Definition: Pericarditis recurrence, for the purpose of the protocol, is defined as the recurrence of typical pericarditis pain associated with supportive objective evidence of pericarditis.

At any time point during the RW period, subjects who experience suspected recurrence of their pericarditis will have been instructed to inform their site Investigator as soon as possible. Subjects who experience a suspected recurrence of pericarditis symptoms will be requested to report to the study site/clinic for a scheduled or unscheduled visit, during which clinical assessments will be performed to gather all the necessary diagnostic data to confirm or rule out the presence of pericarditis recurrence (Section 6.1.4). The Investigator will evaluate all assessments performed for a diagnostic workup, whether at the study site or at locations outside.

Upon completion of pericarditis workup, the Investigator is required to contact the [REDACTED] [REDACTED] medical monitor to confirm that the protocol required diagnostic workup is complete prior to implementing treatment for the event.

[figure not shown]
Following communication with the [REDACTED] medical monitor, if the event meets the criteria for bailout riloncept (at least 1 day with pericarditis pain measurement ≥ 4 on the 11-point NRS and one CRP value ≥ 1 mg/dL either on the same day or separated by no more than 7 days), and after the [REDACTED] medical monitor has confirmed with the Investigator that the diagnostic workup is complete, the attainment of bailout criteria is confirmed in the IWRS, blinded study drug is discontinued, and open-label riloncept treatment is dispensed. If needed, sequential ORT is allowed as outlined in Section 5.6.3. The subject will continue to be followed up according to Section 13.1 for the RW period.

Following communication with the [REDACTED] medical monitor, if the event does not meet the protocol criteria for bailout riloncept but in the judgement of Investigator requires treatment, after the [REDACTED] medical monitor has confirmed with the Investigator that the diagnostic workup is complete, the Investigator is allowed to add sequential ORT to blinded study drug, and as outlined in Section 5.6.3. Blinded study drug treatment will continue until a pericarditis recurrence that meets criteria for bailout riloncept, or until the end of the RW period.

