7.5. Analysis Sets

The following analysis sets will be used in the statistical analyses.

Intent-to-Treat (ITT) Analysis Set: All subjects who are randomized in the RW period will be included in the ITT analysis set. The primary analysis for efficacy endpoints in the RW period will be based on the ITT analysis set. Treatment comparisons for all ITT analyses will be based on each subject's treatment assignment from randomization.

ITT Week 24 analysis set: All subjects randomized at least 24 weeks before data cutoff will be included. This analysis set will be used for secondary efficacy endpoints measured at week 24 in the RW period.

ITT Week 16 analysis set: All subjects randomized at least 16 weeks before data cutoff will be included. This analysis set will be used for secondary efficacy endpoints measured at week 16 in the RW period.

ITT Week 8 analysis set: All subjects randomized at least 8 weeks before data cutoff will be included. This analysis set will be used for secondary efficacy endpoints measured at week 8 in the RW period.

Safety Analysis Set: All subjects who received at least 1 dose of study drug in the RI period will be included in the safety analysis set (SS). Safety analyses will be based on the actual treatment a subject received.

Run-in Analysis Set: All subjects who received at least 1 dose of study drug in the RI period will be included in the RI analysis set (RIS).

Run-in Week 12 Analysis Set: All subjects who received the first dose in the RI period at least 12 weeks before data cutoff. This analysis set will be used for secondary efficacy endpoints measured at Week 12 in the RI period.

Long Term Extension Analysis Set: All subjects who received at least 1 dose of study drug in the long-term extension period will be included in the long-term extension analysis set

Per-protocol Analysis Set: The per protocol (PP) analysis set is a subset of the ITT analysis set with the exclusion of subjects with major protocol violations or violations that may potentially bias statistical analyses or the ethical conduct of the study. The criteria of these violations will be determined prior to unblinding. This analysis set may be used for sensitivity analyses for efficacy endpoints in the RW period.

Pharmacokinetic Analysis Set: The PK analysis set includes subjects who receive at least 1 dose of study drug and have at least 1 PK sample. The PK analysis set will be used for all PK analyses.

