7.7. Statistical Analysis Methodology

This Section outlines the overall methodologies. Details of the statistical analyses, methods, and data conventions will be described in the SAP.

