7.7.1. General Methods

Statistical analysis will be performed using SAS[®] software Version 9.4 or later. Continuous variables will be summarized using the mean, the standard deviation, median, minimum value, and maximum value. Time-to-event variables will be summarized using percent censored, event rate, and 25th, 50th, and 75th percentiles with 95% CI, if estimable.

Categorical variables will be summarized using frequency counts and percentages. Data will be listed in data listings.

At each of RI and RW periods and in the LTE, baseline will be the last value before the first dose of study drug within each individual period unless otherwise specified. For change-over-time endpoints in the RW period, by-visit analysis will be performed at each scheduled visit for at least 24 weeks.

The analysis for treatment comparison will be triggered after at least the 22nd CEC-confirmed pericarditis recurrence events have been accrued. At that time, randomization will be closed, and subjects will return to study sites for the EORW visit. At that point study treatment will stop (completing the database for the primary efficacy endpoint analysis), and subjects will either continue into the LTE or complete their study participation. Missing data due to end of RW period will be considered as missing at random. Handling of missing values will be described in the SAP.

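### Section 7.7.8 compares adverse events by treatment group in the randomized-withdrawal (RW) period, and the only summary measure named is a crude percentage, although bailout shortens blinded time mainly on placebo

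*Protocol*

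**What the plan says.** All references are to Version 3.0 of the protocol unless stated.

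- **Grouping (7.7.8).** "TEAEs will be analyzed for all subjects combined and by treatment group in the RW period". Displays by severity, by relationship and for serious events follow, with no other denominator stated.
- **Measure (7.7.1).** "Categorical variables will be summarized using frequency counts and percentages". Section 7.7.8 names no measure of its own for adverse events beyond confidence intervals where meaningful.
- **Treatment basis (7.5).** "Safety analyses will be based on the actual treatment a subject received".
- **Bailout (3.1.3 and 6.2.3).** A recurrence with pain of at least 4 and CRP of at least 1 mg/dL stops blinded drug and starts open-label rilonacept in either arm. After that, "The subject will continue to be followed up according to Section 13.1 for the RW period".
- **Not every recurrence qualifies (3.1.3).** "Subjects with pericarditis recurrence who do not meet the protocol criteria for bailout rilonacept will continue blinded study drug" until they do, or until the RW period ends.
- **Detail (7.7).** "Details of the statistical analyses, methods, and data conventions will be described in the SAP".

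The one time-based rate that the protocol names is the annualized recurrence rate in 7.3. It names none for adverse events.

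**The concern.** Unequal exposure is built into the design. Section 3.2 expects earlier and more frequent recurrence on placebo, so placebo subjects leave blinded drug sooner. A subject watched for fewer weeks has less chance to report an event. A percentage of subjects with an event does not correct for that.

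Safety is the study's secondary objective: "The secondary objective of this study is to assess the safety of rilonacept treatment in subjects with recurrent pericarditis". The run-in and the long-term extension have no control arm (7.3), so the RW period supplies the only placebo-controlled safety comparison. Section 1.3.1 notes serious, life-threatening infections on rilonacept. An apparent excess produced only by longer observation would therefore be hard to tell from a real one.

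**Working it through.** **Inputs from the protocol (7.4).** Exponential times, placebo median 8 weeks, hazard ratio 0.244, 1-sided 2.5%, power 90%, about 25 subjects per arm.

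**The protocol's own figure.** Events = 4 × (1.960 + 1.282)² / (ln 0.244)² = 21.12, rounded up to 22. This matches 7.4, so the hazards below are the ones the plan was built on.

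**Assumptions, because the protocol gives no figure.**
- RW follow-up t = 24 weeks. Version 3.0 dropped the 24-week minimum.
- Share b of subjects whose recurrence leads to bailout: 100% or 50%.
- Event rate 1.81 per year in both arms. This is the placebo infection rate in the label appended to Version 2.0 (label section 6.3), used for illustration only.

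**Weekly hazards.** Placebo recurrence: ln 2 / 8 = 0.0866. Rilonacept recurrence: 0.244 × 0.0866 = 0.0211. Adverse event: h = 1.81 / 52.18 = 0.0347.

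**Mean blinded time** = b × (1 − exp(−λt))/λ + (1 − b) × t.
- b = 1: placebo (1 − 0.125)/0.0866 = 10.1 weeks; rilonacept (1 − 0.602)/0.0211 = 18.8 weeks.
- b = 0.5: placebo 0.5 × 10.10 + 12 = 17.0 weeks; rilonacept 0.5 × 18.82 + 12 = 21.4 weeks.

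**Percentage with an event on blinded drug, same rate in both arms** = b × h/(h + λ) × (1 − exp(−(h + λ)t)) + (1 − b) × (1 − exp(−ht)).
- b = 1: placebo 0.286 × 0.946 = 27%; rilonacept 0.621 × 0.738 = 46%.
- b = 0.5, with 1 − exp(−24h) = 56.5%: placebo (27.0 + 56.5)/2 = 42%; rilonacept (45.9 + 56.5)/2 = 51%.

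A rate per subject-week would give a ratio of 1.0 in every case.

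**Actual treatment at onset, the reading closest to 7.5.** The placebo column is unchanged. The rilonacept column holds its own arm over all 24 weeks (56.5%) plus placebo subjects after bailout, who number 0.875 × b of the placebo arm. Pooled, the contrast is 27% against 49% for b = 1 and 42% against 52% for b = 0.5. Many placebo subjects then appear in both columns. Attribution is right, but the exposure gap remains.

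**A different bailout model.** The share b treats a subject not bailed out at first recurrence as never bailed out. If instead half of the recurrence hazard leads to bailout, mean blinded time at 24 weeks is 14.9 against 21.2 weeks. The percentages at h = 0.035 are 38% against 51%.

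**Event-driven cut.** The trial was simulated to the 22nd event with 50 to 90 randomized and uniform accrual. With accrual over 26 to 78 weeks, the blinded-time gap was about 6 to 18 points at b = 1 and 3 to 9 points at b = 0.5. If everyone entered on one day, the smallest gap was 1 to 2 points.

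**The case against.** The strongest reply is that this belongs to the SAP, which is not shown. Section 7.7 defers details there, and attribution after a switch and exposure-adjusted rates are ordinary SAP content. Much of that stands. A reader might infer that the protocol prescribes crude percentages as the sole measure for adverse events, or rules out rates. It does neither: 7.7.8 says only that events will be analyzed, the percentages come from the general rule in 7.7.1, and a SAP could add rates without contradiction. What remains is that the one measure the protocol names does not suit the exposure pattern that its own design creates, even on the reading closest to 7.5.

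A reader might also infer that the table would hide real harm, because open-label rilonacept time would sit in the placebo column. That requires grouping the whole RW period by randomized arm, and 7.5 points the other way by basing safety on actual treatment. The argument here does not rest on it.

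The other points are fair. Safety in the RW period is descriptive, and an independent committee reviews unblinded safety data (6.7.1). With 25 per arm, the standard error of a difference in percentages near 40% is √(2 × 0.4 × 0.6/25) = 14 points, so chance alone can exceed part of the range shown. But the exposure effect is systematic and runs in one direction, so it adds to chance rather than averaging out.

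**Conclusion.** The point holds as a modest, cheap improvement to the safety display. On the protocol's own recurrence hazards, blinded exposure at 24 weeks differs by a factor of 1.26 (21.4/17.0) to 1.86 (18.8/10.1). Equal event rates would then appear as a gap of about 9 to 19 points against rilonacept. Across the event-driven scenarios the gap runs from about 1 to 18 points. The direction follows from the design. The size depends on the assumed bailout share, event rate and follow-up, none of which the protocol gives.

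The documents do not support reading this as a threat to the primary test or its 22 events, which are unaffected. Nor do they support a claim that residual rilonacept in the early placebo weeks distorts the comparison. Splitting placebo time at 6 weeks after the last run-in dose would leave too little data to tell carry-over from chance.

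**What to change.** In 7.7.8, keep the by-arm RW table. Add, for all treatment-emergent events, serious events and infections, the number of events, the subject-time and the exposure-adjusted rate for blinded RW time by arm. Show post-bailout open-label time as its own column, so that no subject's open-label time is mixed into either blinded column.

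The cost is one descriptive table. Onset dates (6.4.3), dosing records (5.8) and bailout status (6.2.3) are already collected.

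The rates will be imprecise. At 25 per arm and 1.81 events per year, expected events on blinded drug are 25 × 10.1 × 0.0347 = 8.8 on placebo and 25 × 18.8 × 0.0347 = 16.3 on rilonacept if all recurrences are bailed out. Treating events as Poisson, the 95% limits for the rate ratio are a factor of about exp(1.96 × √(1/8.8 + 1/16.3)) = 2.3 either way. The table removes the exposure artefact; it does not make the comparison precise.

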7.7.9. Interim Analyses

No interim analyses are planned for this study.

8. DATA QUALITY ASSURANCE

Assessment of subject compliance and adherence to study drug administration will be assessed by the site in collaboration with the visiting RN.

This study will be conducted according to the ICH E6(R2) risk and quality processes described in the applicable procedural documents. The quality management approach to be

implemented in this study will be documented and will comply with the current ICH guidance on quality and risk management (ICH Q9).

8.1. Data Management

As part of the responsibilities assumed by participating in the study, the Investigator agrees to maintain adequate case histories for the subjects treated as part of the research under this protocol. The Investigator agrees to maintain accurate eCRFs and source documentation as part of the case histories. These source documents may include laboratory reports, ECG strips, etc.

██████████ will be responsible for activities associated with the data management of this study. This will include setting up a relevant database and data transfer mechanisms, along with appropriate validation of data and resolution of queries. Data generated within this clinical study will be handled according to the relevant Standard Operating Procedures (SOPs) of ██████████

Investigative site personnel will enter subject data into an EDC system. The analysis data sets will be a combination of these data and data from other sources (e.g., laboratory data).

Clinical data management will be performed in accordance with applicable ██████████ standards and data cleaning procedures to ensure the integrity of the data, e.g., removing errors and inconsistencies in the data. Adverse event terms will be coded using MedDRA, an internal validated medical dictionary, and concomitant medications will be coded using the World Health Organization Drug Dictionary.

After the last study database lock, each study site will receive a CD-ROM containing all of their site specific eCRF data as entered into Medidata Rave for the study, including full discrepancy and audit history. Additionally, a Master DVD/CD-ROM copy of all of the site data from the study will be created and sent to Kiniksa for storage. ██████████ will maintain a duplicate Master DVD/CD-ROM copy for their records. In all cases, subject initials will not be collected or transmitted to Kiniksa Pharmaceuticals.

